# 6. Interim Monitoring

Schedule for interim analyses (at every  $1/3^{rd}$  of total patients enrolled) will be finalized in consultation with the Data Safety Monitoring Committee (DSMC). The overall principle of interim analyses is to determine early if tenecteplase causes more mortality or is significantly inferior to alteplase at interim. Early stopping of the trial for efficacy is generally to be avoided. The guidance on stopping for safety pertains to a substantial mortality difference favoring alteplase at interim. This may be met if the observed p-value for mortality comparing the two randomized groups is below a threshold defined using a power family approach to alpha-spending using  $\phi$ =1, and if the numeric rate of mortality favors alteplase (e.g., if it is found that tenecteplase is substantially and significantly inferior to alteplase in terms of mortality at interim). For inferiority of tenecteplase, the stopping may be defined in terms of absolute difference between the tenecteplase and alteplase rates of mRS 0-1 at 90-120 days. As an example, if at interim, the difference  $\Delta$  for mRS 0-1 at 90-120 days in the tenecteplase vs. alteplase group is lower (worse) than an indicated value (see table in DSMC Charter for some suggested thresholds), the trial may be stopped for significant inferiority of tenecteplase. Details are provided in the AcT trial DSMC charter.

## 7. Definition of the target populations

7.1. Intention to Treat population All patients enrolled in the trial randomized on an intent-to-treat basis.

7.2. Per-protocol population

All patients enrolled in the trial who received any dose of study drug and met all the inclusion and exclusion criteria per current Canadian Stroke Best Practices Recommendations. Since the trial has pragmatic eligibility criteria, patients who may have been inadvertently enrolled and received thrombolysis beyond 4.5 hours from stroke onset and any treatment crossovers are defined as protocol deviations for analysis.

Page 4 of 9

## 8. Blinding

Treatment assignment is open label. Blinding of the outcome assessment at 90-120 days will be ensured by having central personnel trained on administration of the Rankin Focused Assessment, blinded to treatment allocation, and not involved in the acute treatment period conduct the assessment via telephone.

## 9. Statistical Analysis

Primary analysis of the trial data to establish non-inferiority will be conducted using risk difference analysis. First, non-inferiority will be established if the lower boundary of the 95% confidence interval of the percentage difference in subjects achieving excellent outcome (mRS 0-1) in the tenecteplase versus the alteplase arm is greater than – 5% (the non-inferiority margin). If non-inferiority is demonstrated, then a test of superiority of tenecteplase vs. alteplase will be performed as part of secondary analysis. In addition, logistic regression will be used to provide an adjusted estimate of the effectiveness of tenecteplase over alteplase for the primary outcome. The risk ratio of good 90-day outcome (mRS01) associated with the treatment groups will be estimated using a mixed-effects logistic regression model that adjusts for age, sex, baseline stroke severity, and stroke onset-to-needle time as fixed effects, and site, and registry (QuiCR vs. OPTIMISE) as random effects.

Secondary analyses will evaluate key safety (mortality and symptomatic intracerebral hemorrhage as defined in the AcT trial MOP) and secondary outcomes using relevant tests of association. Frequency tables will be used to summarize categorical variables by treatment group. Descriptive statistics will be used to summarize continuous data variables by treatment group.

The secondary outcomes and the corresponding analyses are described as follows. Both unadjusted (not described in Table below) and adjusted (described in table below) will be reported. Unadjusted analysis will be tests of difference in proportions, means or medians or regression analysis as appropriate. All analyses will be conducted secondary analyses are conducted at  $\alpha$  = 0.05.

Outcome	Analysis
mRS 0-1 i.e., excellent	Efficacy secondary analysis of the mRS 0-1.
functional outcome (blinded)	Logistic mixed-effects regression model with
	treatment (Tenecteplase vs Alteplase) as
	exposure; age, sex, baseline stroke severity, and
	stroke onset-to-needle time as fixed effects, and
	site, and registry (QuiCR vs. OPTIMISE) as random
	effects.
mRS 0-2 i.e., good functional	Risk difference and the corresponding 95%CI to
outcome (blinded)	assess non-inferiority. Risk ratio and the 95%CI to
	evaluate efficacy

Page 5 of 9

	Adjusted logistic mixed-effects regression model with treatment (Tenecteplase vs Alteplase) as exposure; age, sex, baseline stroke severity, and stroke onset-to-needle time as fixed effects, and site, and registry (QuiCR vs. OPTIMISE) as random effects.
Ordinal mRS (blinded)	Ordinal logistic mixed-effects regression with treatment (Tenecteplase vs Alteplase) as exposure; for age, sex, baseline stroke severity, and stroke onset-to-needle time as fixed effects, and site, and registry (QuiCR vs. OPTIMISE) as random effects.
Return to pre-stroke status (pragmatic outcome) (blinded)	Risk difference and the corresponding 95%CI to assess non-inferiority. Risk ratio and the 95%CI to evaluate efficacy
	Adjusted logistic regression analysis with treatment (Tenecteplase vs Alteplase) as exposure; age, sex, baseline stroke severity, and stroke onset-to-needle time as fixed effects, and site, and registry (QuiCR vs. OPTIMISE) as random effects.
Euroqol 5-D Visual Analogue Scale (EQ5D-VAS) (blinded)	A linear mixed-effects regression model with treatment (Tenecteplase vs Alteplase) as exposure; age, sex, baseline stroke severity, and stroke onset-to-needle time as fixed effects, and site, and registry (QuiCR vs. OPTIMISE) as random effects.
EQ5D-5L (blinded)	Adjusted and unadjusted ordinal logistic regression analyses will be conducted for each EQ5D item (mobility, self-care, usual activities, anxiety, and depression) as the outcome variable.
	Health utility index derived from the EQ5D-5L items.
	Linear regression analysis with robust standard errors with treatment (Tenecteplase vs Alteplase) as exposure; age, sex, baseline stroke severity, and stroke onset-to-needle time as fixed effects,

Page 6 of 9

	Q
	and site, and registry (QuiCR vs. OPTIMISE) as
	explanatory variables.
Home time*	A generalized linear mixed-effects regression model with treatment (Tenecteplase vs Alteplase) as exposure; age, sex, baseline stroke severity, and stroke onset-to-needle time as fixed effects, and site, and registry (QuiCR vs. OPTIMISE) as random effects.
	In addition to home time, similar exploratory analysis will be conducted for other registry and administrative data outcomes such as length of hospital stay until discharge and discharge destination (home, home with home care, home with early supportive discharge, rehabilitation hospital, long term care and hospice) that will use appropriate regression analysis.
Mortality	Risk difference and the corresponding 95%CI
	A Kaplan-Meier survival distribution. Patients alive after 90/120 days were censored. Logistic mixed-effects regression model with treatment (Tenecteplase vs Alteplase) as exposure; age, sex, baseline stroke severity, and stroke onset-to-needle time as fixed effects, and site, and registry (QuiCR vs. OPTIMISE) as random effects.
Symptomatic intracerebral hemorrhage	Risk difference and the corresponding 95%CI
	Logistic mixed-effects regression model with
	treatment (Tenecteplase vs Alteplase) as
	exposure; age, sex, baseline stroke severity, and
	stroke onset-to-needle time as fixed effects, and site, and registry (QuiCR vs. OPTIMISE) as random effects.
Intracranial Hemorrhage on follow-up Imaging (Blinded)	Difference in proportion of ICH categories and the corresponding 95%Cl

Page **7** of **9** 

 
Parenchymal hemorrhage (hemorrhagic infarction type 1, hemorrhagic infarction type 2, parenchymal hematoma type 1, parenchymal hematoma type 2, remote hemorrhagic infarction type 1, remote hemorrhagic infarction type 2, remote parenchymal hematoma type 1, remote parenchymal hematoma type 1, remote parenchymal hematoma type 2)
 
Subdural hemorrhage
 
Subarachnoid hemorrhage
 
Intraventricular
 
	
Peripheral Bleeding requiring Blood Transfusion	Risk difference and the corresponding 95%CI
Angioedema	Risk difference and the corresponding 95%Cl
Proportion of patients receiving EVT	Risk difference and the corresponding 95%CI.
	Logistic mixed-effects regression model with
	treatment (Tenecteplase vs Alteplase) as
	exposure; age, sex, baseline stroke severity, and
	stroke onset-to-needle time as fixed effects, and site, and registry (QuiCR vs. OPTIMISE) as random effects.
Other SAEs and SUSARs	Risk difference and the corresponding 95%CI

Page **8** of **9** 

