#### 5.3 Proposed practical arrangements for allocating participants to trial groups

Eligible patients will be randomized in a 1:1 ratio. Randomization will use a validated minimal sufficient balance (MSB) algorithm, to assure balance by site. The algorithm will kick in after the site has enrolled 5 subjects. The standard distribution is 50-50, but when an imbalance is detected with a p-value less than 0.3, the distribution changes to 65-35 in the direction against the imbalance. Randomization will be centralized, secure and concealed using a real-time web-based server, thus eliminating the possibility of confounding due to allocation bias. The central server will be linked to a randomization mechanism and will only be able to allocate one patient to either arm of the trial at one time. Investigators will be able to rapidly access the randomizer through a secure internet web browser or secure automated phone number or text message. Investigators will have to enter a site-specific ID number followed by an Investigator specific ID number and the weight of the patient in kilograms. They will then receive the drug allocation (tenecteplase vs. alteplase) along with unique study subject ID and the calculated drug dosage. They will later be prompted to enter if a) the correct drug was administered b) the correct dose was administered and c) the vial LOT number and expiry date of the administered drug.

Emails will be sent from the central trial server to site investigators and trial personnel with the site ID, unique study subject ID and drug allocation (study enrolment form). A copy of this email can be

printed and included in the patient chart. In addition, this email will also have a PDF checklist reminding site co-ordinators to ensure the following

- 1. The study enrolment form is placed in the clinical patient chart
- 2. The patient and surrogate contact information is documented in the checklist
- 3. Consent is obtained (see section 5.4) and documented in the study database
- 4. The unique study subject ID and registry ID are entered in the study database
- 5. Report any serious adverse events occurring within the first 24 hours of randomization. This information will be documented on paper and/or in the study database

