#### 6.6 Proposed types of analyses

Primary efficacy analysis will be intention to treat. Given pragmatic eligibility criteria and up-front one-time treatment, we expect no cross-overs and very few protocol violations. A protected hierarchical analysis plan will be performed. First, non-inferiority will be established if the lower boundary of the 95% confidence interval of the % difference in subjects achieving good outcome (mRS 0-1) in the tenecteplase versus the alteplase arm is greater than -5% (the non-inferiority margin). If non-inferiority is demonstrated, then a test of superiority will be performed as part of secondary analysis. The primary analysis for efficacy will be a stratified Cochran-Mantel-Haenszel (CMH) test where registry (QuICR vs. OPTIMISE) will be used as a stratification variable. If noninferiority is not demonstrated, all subsequent analyses will be considered hypothesis-generating. As sensitivity analysis, logistic regression will be used to provide an adjusted estimate of effect size of the effectiveness of tenecteplase over alteplase. The odds ratio of good 90-day outcome associated with the treatment groups will be estimated using a logistic regression model after adjusting for registry, age, sex, baseline stroke severity and onset-to-needle time. For secondary analyses, frequency tables will be used to summarize binary variables by treatment group. Descriptive statistics will be used to summarize continuous data variables by treatment group. Similar to the primary efficacy variable, binary secondary outcomes will be analyzed using logistic regression analysis. The continuous secondary outcomes will be analyzed using analysis of covariance (ANCOVA) and mixed-effects regression with the registry (QuICR vs. OPTIMISE) variable treated as a randomeffect. If non-inferiority of the primary outcome is demonstrated, a hierarchical multiplicity

adjustment will be used to determine the Type I error for testing the secondary outcomes in order to control the overall familywise type I error rate for the study. Sex will be a unit of analysis. In addition, given previous literature suggesting underutilization of thrombolysis in females, sex-based differences in recruitment, workflow and processes and outcomes will constitute important prespecified subgroup analyses. Details will be provided in the statistical analysis plan that will be developed and reviewed by the trial steering committee.

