#### 4. Randomization

Randomization will be centralized, secure and concealed using a real-time web-based server, to prevent confounding due to allocation bias. Investigators can access the randomizer either through the internet, secure text or through a local telephone. The trial will have allocation concealment and blinded endpoint assessment. Given the pragmatic design of the trial and the time sensitive nature of acute stroke, blinding the enrolling health personnel to treatment allocation is not practical. A 1:1 randomization will be used to allocate patients to intravenous tenecteplase (0.25 mg/kg body weight, max dose 25 mg) or intravenous alteplase (0.9 mg/kg body weight, max dose 90 mg). Randomization will use a validated minimal sufficient balance (MSB) algorithm to assure balance by site.

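### One non-inferiority rule but two unreconciled primary methods, and no baseline adjustment on the risk-difference scale: the cost is precision, not validity

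*Combined protocol and SAP*

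**What the plan says.** **Decision rule.** Protocol 6.6 states that "non-inferiority will be established if the lower boundary of the 95% confidence interval of the % difference in subjects achieving good outcome (mRS 0-1") is above -5%. SAP section 9 gives the same rule, apart from calling the outcome excellent rather than good.

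**Primary method.** After the non-inferiority rule and the superiority step, protocol 6.6 adds: "The primary analysis for efficacy will be a stratified Cochran-Mantel-Haenszel (CMH) test where registry (QuICR vs. OPTIMISE) will be used as a stratification variable". SAP section 9 has no such test. It says "Primary analysis of the trial data to establish non-inferiority will be conducted using risk difference analysis", with no estimator, stratification or interval method, and does not mention that the CMH test has been dropped.

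**Randomisation.** Protocol 5.3 and SAP section 4 both balance on site only: "Randomization will use a validated minimal sufficient balance (MSB) algorithm to assure balance by site".

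**Adjusted models.** Protocol 6.6 has a sensitivity logistic model giving an odds ratio "after adjusting for registry, age, sex, baseline stroke severity and onset-to-needle time". SAP section 9 adds a "mixed-effects logistic regression model that adjusts for age, sex, baseline stroke severity, and stroke onset-to-needle time as fixed effects, and site, and registry" as random effects, reported as a risk ratio. Neither yields an adjusted risk difference.

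**The concern.** The whole trial turns on one confidence bound set against -5 points, and a reader cannot tell from the two documents how that bound will be computed. A CMH test asks whether the arms differ at all. It gives no answer about a difference of -5 points unless it is replaced by a stratum-weighted risk difference with an interval.

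Separately, the trial balances on site and collects strong candidate predictors of mRS 0-1 (age and baseline NIHSS), but uses none of them in the deciding analysis. What is at stake is the width of that interval, and the freedom to choose among methods if the choice is left open until the data are seen.

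**Working it through.** **Inputs from the documents.** 38% vs 35%, margin 5 points, one-sided alpha 2.5%, power 90%, 759 per arm, 1600 in total, loss below 5% (protocol 6.1, SAP section 5). Site balancing moves allocation to 65:35 when the imbalance p-value is below 0.3, after 5 patients at a site (protocol 5.3).

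**Input not in the documents.** R², the share of outcome variance explained by baseline covariates, is assumed to be 0.05 to 0.30.

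**1. Reproduce the plan.** With an unadjusted risk difference and unpooled variance:

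n per arm = (z_α + z_β)² × [0.38×0.62 + 0.35×0.65] / (0.03 + 0.05)²

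- With 1.96 and 1.2816: 10.508 × 0.4631 / 0.0064 = 760.3.
- With 1.96 and 1.28: 759.6, in line with the stated 759.
- Allowing for loss: 759 / 0.95 = 799 per arm, about 1598, stated as 1600.

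The example in protocol 6.1 (34.7% vs 35%) also fits an unadjusted interval. With 800 per arm, SE = √[(0.347×0.653 + 0.35×0.65)/800] = 0.0238, and -0.3 - 1.96×2.38 gives -4.97 points (stated -4.96). With 759 per arm the bound would be -5.09. The design was therefore sized on an unadjusted, unstratified difference, and its 90% power does not depend on adjustment.

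**2. Does the choice between the two named methods matter numerically?** Trials of 1600 patients were simulated under the site-balancing rule (1,200 to 1,500 runs per setting). Assumed settings were 22 sites, a site SD of 0.3 and a registry effect of 0.2 on the logit scale, and R² about 0.18 from age and severity. The adjusted model contained age, severity and registry.

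| Estimator | Mean SE (38% vs 35%) | Non-inferiority shown (38% vs 35%) | Non-inferiority shown (true difference -5) |
|---|---|---|---|
| Unadjusted risk difference | 0.0240 | 91.9% | 2.3% |
| Registry-stratified Mantel-Haenszel risk difference | 0.0240 | 91.8% | 2.3% |
| Standardised, adjusted risk difference | 0.0219 | 96.3% | 1.9% |

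Registry stratification changes almost nothing. Leaving out site did not inflate type I error. With 1,500 runs the simulation error is √(0.025×0.975/1500) = 0.4 points, so 2.3% and 1.9% are both compatible with 2.5%. Adjustment shrinks the SE by 1 - 0.0219/0.0240, about 9%.

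**3. What adjustment is worth.** Multiply the variance by (1 - R²). At 760 per arm, the unadjusted SE is √(0.4631/760) = 0.0247 at 38% vs 35% and √(0.455/760) = 0.0245 at equal rates of 35%. Power = Φ[(d + 0.05)/(SE√(1 - R²)) - 1.96], where d is the true difference.

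| R² (assumed) | CI half-width, points (38 vs 35) | Power, 38 vs 35 | Power, 35 vs 35 |
|---|---|---|---|
| 0 | 4.84 | 90.0% | 53.3% |
| 0.05 | 4.72 | 91.4% | 55.4% |
| 0.10 | 4.59 | 92.7% | 57.7% |
| 0.20 | 4.33 | 95.2% | 62.7% |
| 0.30 | 4.05 | 97.2% | 68.5% |

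The gain is about 1 to 7 power points at the design alternative, and about 2 to 15 if the drugs are equal.

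**The case against.** The best defence is that there is one rule, not two. Endpoint, scale, confidence level and margin agree. The CMH sentence follows the superiority step and speaks of efficacy, so it may never have been meant as the non-inferiority test. Protocol 6.6 also leaves details to the SAP. A registry-stratified Mantel-Haenszel risk difference would satisfy both texts with practically the same result. Both documents pre-specify an adjusted model for this same endpoint, the SAP's with site, and the trial is powered without adjustment.

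Most of this stands, and it sets the limits of the point. Three things remain:

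- The SAP omits the CMH test without saying so. If that test belongs only to superiority, then neither document names a method for the non-inferiority interval.
- The adjusted models give an odds ratio (protocol) or a risk ratio (SAP). A logistic model yields an odds ratio directly, and the SAP states no conversion. Neither result can be set against a 5-point margin.
- Registry has two levels in both plans, yet protocol 5.1 and 6.5 allow sites that are in neither registry. Those patients have no stratum.

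A fair caution is that adjustment adds choices, such as how to treat small sites and missing covariates. These must be fixed in advance.

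**Conclusion.** The primary method needs to be stated once and reconciled, and a more precise estimator is available at no patient cost. This is a should-fix and a free improvement, not a flaw that invalidates the trial. The size of the gain rests on an R² the documents do not give.

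Three stronger readings are tempting, and the documents do not support them:

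- *A reader might infer that the two documents set incompatible tests, one of which cannot test the hypothesis.* That holds only if the CMH sentence is read as replacing the explicit interval rule in the same section. Also, the SAP never calls its risk difference crude. That is inferred from the adjusted model being listed as an addition.
- *A reader might infer that ignoring site or covariates makes the test invalid or the trial underpowered.* The stated 759 and 90% reproduce unadjusted, and simulated type I error was about 2.3%. No separate loss from omitting site was shown.
- *A reader might blame missing covariates for the 53% power under equal rates.* That figure follows from sizing the trial on a 3-point advantage for tenecteplase. Adjustment lifts it only to about 55-69%.

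**What to change.** In SAP section 9 and protocol 6.6, before unblinding:

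1. Name one primary estimator: the standardised (g-computation) risk difference from a logistic working model with treatment, age, sex, baseline NIHSS and site or registry. Give its 95% interval by the delta method or bootstrap, and compare the lower bound with -5 points.
2. State a pooling rule for small sites, or, if registry is used, a category for sites in neither registry. State a rule for missing baseline values.
3. Leave onset-to-needle time out of this model. The needle follows randomisation (protocol 5.2), and door-to-needle time is itself a secondary outcome (protocol 5.9), so the covariate could be affected by treatment.
4. Keep the unadjusted risk difference, with a named interval method, as the first supportive analysis.
5. Say that this supersedes the CMH sentence. If a CMH-type analysis is kept, report its stratum-weighted risk difference as supportive only.

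Cost: wording in two documents and modest programming. No new patients, and no data beyond what the adjusted models already require.

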# 5. The Proposed Trial

# 5.1 Trial design

The proposed trial is a pragmatic, registry based, prospective, randomized (1:1) controlled, open-label parallel group clinical trial with blinded endpoint assessment of 1600 patients to test if intravenous tenecteplase (0.25 mg/kg body weight, max dose 25 mg) is non-inferior to intravenous alteplase (0.9 mg/kg body weight, max dose 90 mg) in patients with acute ischemic stroke otherwise eligible for intravenous thrombolysis as per standard care.

The trial will be **embedded within the QuICR and the OPTIMISE registries**. It will use linkages to administrative datasets to collect relevant data not available through the registries.

QuICR (https://www.ucalgary.ca/quicr/) is a cloud-based registry that collects data on all ischemic stroke patients receiving thrombolysis and/or endovascular treatment in Alberta. Currently, all stroke centres in Alberta and one primary stroke center (PSC) in Saskatchewan are contributing to the registry. The registry includes 15 PSCs that provide intravenous thrombolysis treatment only, and 2 Comprehensive Stroke Centres (CSCs) that provide both thrombolysis treatment and endovascular treatment. If possible, we will also utilize the Stroke Ambulance centred in Edmonton at the University of Alberta Hospital (16th PSC) and the Northern Alberta tele-stroke network (currently participating in QuICR)

OPTIMISE is a national registry supported by the Canadian Stroke Consortium to support the implementation and quality control for endovascular therapy (and more recently intravenous thrombolysis) among patients with acute ischemic stroke. The data collection fields in OPTIMISE were designed to mirror the QuICR registry. Data is captured using a web-based electronic data capture and reporting system and housed on a secure server at the Population Health Research Institute (PHRI) at McMaster University.

All sites participating in QuICR will participate in the trial. Sites participating in OPTIMISE and collecting data on all thrombolysis patients will also participate in the trial. In addition, other CSCs or PSCs in Canada that agree to participate in either the QUICR or the OPTIMISE registries or have similar infrastructure will also be eligible to participate in the trial.

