#### 6.5 Centers involved

The QuiCR registry currently includes 15 Primary Stroke Centers that provide thrombolysis treatment only, and 2 Comprehensive Stroke Centers that provide both thrombolysis treatment and endovascular treatment. OPTIMISE registry sites will also be participating. All QuICR and OPTIMISE sites, as well as additional sites, will be eligible to participate in this study if they a) are actively participating or agree to participate in one of the two registries or b) have regular institutional reporting/contribution of data to administrative datasets (e.g. Discharge Abstract Database) that can be accessed and linked to trial outcomes as per statistical analysis plan, and c) obtain local REB/IRB approval.

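### SAP section 9 promises an adjusted risk ratio from a mixed-effects logistic model but states no step that yields one; two-level registry is also a poor random effect with no stated value for sites in neither registry

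*Combined protocol and SAP*

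**What the plan says.** **Effect measure.** SAP section 9 bases the non-inferiority decision on a risk difference for mRS 0-1. It then adds an adjusted analysis of the same outcome: "The risk ratio of good 90-day outcome (mRS01) associated with the treatment groups will be estimated using a mixed-effects logistic regression model". Age, sex, stroke severity and onset-to-needle time are fixed effects, with "site, and registry (QuiCR vs. OPTIMISE) as random effects". No standardisation, log link or Poisson model is mentioned. Protocol 6.6 describes its adjusted sensitivity analysis of the same outcome differently: "The odds ratio of good 90-day outcome associated with the treatment groups will be estimated using a logistic regression model after adjusting for registry", together with the same four covariates.

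**Role of registry.** In the SAP section 9 table, site and registry are random effects for nine outcomes: mRS 0-1, mRS 0-2, ordinal mRS, return to pre-stroke status, EQ5D-VAS, home time, mortality, symptomatic intracerebral haemorrhage and receipt of EVT. The EQ5D-5L utility model instead enters both as explanatory variables. Protocol 6.6 uses registry in three ways: as a covariate in the logistic model, as a random effect for continuous secondary outcomes, and in the CMH analysis, "where registry (QuICR vs. OPTIMISE) will be used as a stratification variable".

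**Which sites may take part.** Protocol 6.5 accepts sites that join a registry or, alternatively, "have regular institutional reporting/contribution of data to administrative datasets". Protocol 5.1 accepts centres that join a registry "or have similar infrastructure will also be eligible to participate in the trial". Protocol 5.6 speaks only of hospitals in the two registries. Neither document says what value the registry variable takes for a site in neither.

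**The concern.** A logit-link model does not return a risk ratio as its coefficient. With about one patient in three expected to reach mRS 0-1, the odds ratio is not a fair approximation to the risk ratio. The two documents name different effect measures for the same supportive analysis, and the SAP leaves open which number will appear under the label risk ratio. An analyst who exponentiates the coefficient and follows the SAP's label would report a treatment effect further from 1 than the true risk ratio. Leaving the choice of measure until after the data are seen is also undesirable in an open-label trial.

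The registry term raises two smaller questions: whether a variance can usefully be estimated from two levels, and what happens to randomised patients for whom the variable has no defined value.

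**Working it through.** **1. The plan's own figure.** Inputs from SAP section 5: p1 = 0.38 (tenecteplase), p0 = 0.35 (alteplase), margin 0.05, one-sided alpha 0.025, power 90%.

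n per arm = (1.960 + 1.282)² × (0.38×0.62 + 0.35×0.65) / (0.03 + 0.05)² = 10.507 × 0.4631 / 0.0064 ≈ 760.3, so 761. The plan states 759, which agrees closely. Allowing for 5% loss, 2 × 759 / 0.95 gives 1,598 against 1,600 planned. Nothing below alters these figures.

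**2. Odds ratio against risk ratio at the documents' rates.**

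RR = p1/p0; OR = [p1/(1−p1)] / [p0/(1−p0)] = RR × (1−p0)/(1−p1).

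| Source of rates | p1 | p0 | RR | OR |
|---|---|---|---|---|
| Design assumption (SAP 5, protocol 6.1) | 0.38 | 0.35 | 1.086 | 1.138 |
| Five-trial meta-analysis (protocol 4.5.1) | 0.579 | 0.554 | 1.045 | 1.107 |

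For the first row: RR = 0.38/0.35 = 1.0857; OR = (0.38/0.62)/(0.35/0.65) = 0.6129/0.5385 = 1.1382. The excess over 1 is 13.8% rather than 8.6%, a ratio of 0.1382/0.0857 = 1.61.

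**3. Can a risk ratio come from a logistic fit?** This was checked by simulation: 200,000 patients, true marginal rates 35% and 38%, and two standardised prognostic covariates with assumed logit coefficients −0.5 and −0.9. There were no site or registry effects. The true conditional OR was 1.170 and the fitted one 1.148. Predicting every patient under each treatment from that same fit and averaging gave a risk ratio of 1.075 and a risk difference of 0.026. The gap from the true 1.086 and 0.03 is sampling error. So a logistic model can supply a risk ratio, given one further step. With prognostic covariates the conditional OR can also lie further from the risk ratio than the crude OR does.

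**4. Information about the registry variance.** Two levels leave 1 degree of freedom. Even if the two registry effects were observed without error, the 95% limits for their SD would be the estimate times √(1/χ²₀.₉₇₅,₁) = 0.45 to √(1/χ²₀.₀₂₅,₁) = 31.9. Under an assumed layout (600 and 1,000 patients, 20 and 25 sites, site SD 0.3 on the logit scale), the share of simulated trials with a registry variance estimate of exactly zero was:

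| True registry SD | REML-like | ML-like |
|---|---|---|
| 0 | 68% | 84% |
| 0.1 | 52% | 68% |
| 0.2 | 34% | 47% |
| 0.3 | 25% | 35% |

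**5. Non-registry sites.** Set side by side, protocol 5.1 and 6.5 permit them, 5.6 does not mention them, and the variable used in the SAP has two named levels. The documents do not give the number of patients who could be affected.

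**The case against.** Several stronger readings are tempting, and the documents do not support them.

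- *The model cannot produce a risk ratio.* A reader might infer this from the word logistic. Step 3 shows otherwise: standardisation gets there. What is missing is a stated step, and the two documents disagree on the measure.
- *The effect will be overstated by 61%.* That follows only if the exponentiated coefficient is printed as a risk ratio, which the SAP does not say will be done. For mRS 0-2 and return to pre-stroke status the SAP lists a risk ratio separately from the adjusted logistic model, so it does not generally treat the two as one.
- *The non-inferiority conclusion is at risk.* It is not. The SAP judges the margin on a risk difference, and the adjusted model never tests it.
- *The registry random effect destabilises the treatment estimates.* This has not been shown. If the variance is estimated as zero, the model reduces to one with a site intercept only, which is a sound model. Randomisation also seeks balance by site, so treatment should be close to balanced across registries. Some analyses carry no registry model at all, among them imaging haemorrhage, peripheral bleeding and angioedema.
- *Patients at non-registry sites will be dropped.* That needs such sites to enrol, their registry value to be set to missing, and incomplete rows to be deleted. None of the three is stated. Protocol 7.2 and 7.4 assume that each patient has a registry record, and SAP section 11 keeps all remaining randomised patients under intention to treat and foresees multiple imputation.

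What stands after this: the effect-measure mismatch is on the page, the missing step is material for an outcome this common, and the coding of registry is undefined for sites that the protocol admits.

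**Conclusion.** The point holds as a defect of specification in a supportive analysis. SAP section 9 labels as a risk ratio the output of a model whose coefficient is a log odds ratio, gives no conversion, and conflicts with protocol 6.6. At the planned rates the difference is 1.14 against 1.09, on the condition that the coefficient is reported unconverted and ignoring covariate adjustment, which can widen the gap. The primary risk-difference test and the sample size are untouched.

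The registry point is secondary. Two levels tell almost nothing about a variance, so a random effect is the weaker choice, but no harm to the treatment estimate is demonstrated. The zero-variance shares depend on an assumed layout. Loss of patients from non-registry sites is a contingency to guard against, and its size cannot be judged from the documents. The point is worth settling before the data are analysed.

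**What to change.** 1. In SAP section 9, name the method for the adjusted risk ratio. Either use marginal standardisation from the logistic model, reporting the adjusted risk difference as well, and state how site effects are handled in the averaging and how the interval is obtained (delta method, or a bootstrap that resamples sites); or use modified Poisson regression with robust errors clustered by site. Label every logistic coefficient as an odds ratio.
2. Bring SAP section 9 and protocol 6.6 to the same effect measure for this analysis.
3. Keep site as the random effect in the adjusted models. Enter registry as a fixed effect or drop it, and do so consistently across the table.
4. Define a registry level for sites in neither registry, so that if any enrol their patients stay in the adjusted models. The same definition would serve the registry subgroup in SAP section 10 and the CMH stratum in protocol 6.6. Reconcile protocol 5.6 with 5.1 and 6.5.

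The cost is SAP wording and minor programming. No additional patients, data collection or change in clinical conduct is needed.
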